4.3. Selection of Study Population

4.3.1. Inclusion Criteria

4.3.1.1. Randomized Cohort

- Must be ≥ 15 years of age at the time of enrollment
- Must be able to provide written consent and complete the informed consent
- Must have received allogeneic hematopoietic cell transplantation within 60-180 days prior to randomization
- CMV seropositive or had a donor who was CMV positive
- One or both of the following:
 - CMV event¹ within the first 100 days post-transplant requiring anti-viral treatment.
 - Receipt of CMV prophylaxis² prior to randomization. Continuation of letermovir or acyclovir/valacyclovir (high and low dose) prophylaxis after day 100 per institutional standard of care is permitted.

¹ CMV event defined as DNA detection or disease

² Anti-viral treatment or prophylaxis includes ganciclovir, valganciclovir, foscarnet, letermovir, maribabir or acyclovir/valaclycovir (high and low dose)

- Direct availability to the internet either by a computer in the residence or a smart phone
- Had at least one or more of these conditions:
 - HLA mismatch³
 - Umbilical cord blood source⁴
 - Graft versus host disease (GVHD)⁵
 - T-cell depletion⁶

³ Human leukocyte antigen (HLA)-related(sibling) donor with at least one mismatch at one of the following three HLA-gene loci: HLA-A, -B or -DR, Haploidentical donor, Unrelated donor with at least one mismatch at one of the following four HLA-gene loci: HLA-A, -B, -C and -DRB1 ⁴ Use of umbilical cord blood as stem cell source

⁵ Acute or chronic GVHD requiring topical steroid for gastrointestinal (GI) GVHD and/or systemic steroid treatment (>1mg/kg/day of prednisone or equivalent dose of another corticosteroid) within 6 weeks prior to enrollment

⁶ Participants who have received partial or full T-cell depletion (with or without GVHD). T-cell depletion can be given as either ex-vivo or in-vivo for GVHD prophylaxis. T-cell depleting agents include, but are not limited to, ATG and alemtuzumab.

4.3.1.2. Observational Cohort

- Must be ≥ 15 years of age at the time of enrollment
- Must have one of the following:
 - Consented for retrospective studies at their transplant center, or
 - Be included under the auspices of the site's IRB approved waiver of additional consent for retrospective studies
- Must have received allogeneic hematopoietic cell transplantation during or within 1 year prior to the conduct of the randomized trial (defined as time during which randomization is done).
- CMV seropositive or had a donor who was CMV positive
- One or both of the following:
 - CMV event¹ within the first 100 days post-transplant requiring anti-viral treatment.

- Receipt of CMV prophylaxis² (for at least 30 days) prior to registration. Continuation of letermovir prophylaxis or acyclovir/valacyclovir (high and low dose) after day 100 per institutional standard of care is permitted.

¹ CMV event defined as DNA detection or disease

² Anti-viral treatment or prophylaxis includes ganciclovir, valganciclovir, foscarnet, letermovir, maribavir or acyclovir/valacyclovir (high and low dose)

- Meet one or more criteria of the following:
 - HLA mismatch³
 - Umbilical cord blood source⁴
 - GVHD⁵
 - T-cell depletion⁶

³ Human leukocyte antigen (HLA)-related(sibling) donor with at least one mismatch at one of the following three HLA-gene loci: HLA-A, -B or -DR, Haploidentical donor, Unrelated donor with at least one mismatch at one of the following four HLA-gene loci: HLA-A, -B, -C and -DRB1

⁴ Use of umbilical cord blood as stem cell source

⁵ Acute or chronic GVHD requiring topical steroid for GI GVHD and/or systemic steroid treatment (>1mg/kg/day of prednisone or equivalent dose of another corticosteroid) within 6 weeks prior to enrollment

⁶ Participants who have received partial or full T-cell depletion (with or without GVHD). Tcell depletion can be given as either ex-vivo or in-vivo for GVHD prophylaxis. T-cell depleting agents include, but are not limited to, anti-thymocyte globulin (ATG) and alemtuzumab.

4.3.2. Exclusion Criteria

4.3.2.1. Randomized Study

- Inability to fully comprehend the study website and study procedures
- Any other condition which in the opinion of the investigator would interfere with successful completion of this clinical trial
- Morphological relapse (bone marrow or peripheral blood blast) prior to registration.

4.3.2.2. Observational Cohort

- Did not meet all inclusion criteria
- Morphological relapse (bone marrow or peripheral blood blast) prior to registration

4.4. Interventions

4.4.1. Intervention Administered

In the randomized cohort, participants will be randomized to weekly participant collection of DBS samples with mobile technology support or to no intervention (standard of care, SOC). Participants randomized to both the DBS arm and the SOC arm completed standard of care CMV monitoring at the clinician-recommended interval with samples collected and tested by the clinical care team, the results of which are recorded in the medical chart.

Participants randomized to the DBS arm conducted weekly DBS testing. They received weekly text message or email reminders to complete the DBS testing. Participants in the DBS arm were also be notified by text message or email if a positive result for a DBS sample was entered into the data system by the study laboratory. If a positive result was reported, the participant was required to have a confirmatory whole blood sample collected by their clinical team, as well as a confirmatory DBS sample, which were both mailed to the study lab for testing.

There were no interventions in the observational cohort. The results of clinician-recommended monitoring were not collected in the observational cohort. This cohort was included to assess the incidence of late CMV disease in the population.

4.4.2. Identity of Investigational Product(s)

The study intervention is the combination of weekly DBS monitoring along with text or email DBS monitoring reminders and text or email notifications of positive DBS test results.

Participants in the DBS arm will receive DBS self-collection and WB collection kits. The DBS self-collection kits will be assembled, packaged and distributed to each enrolling site by Fred Hutchinson Cancer Research Center; the kit will be stored and shipped at room temperature. Participants are responsible for ordering additional self-collection kits.

4.4.3. Method of Assigning Participants to Intervention Groups (Randomized or Observational Cohort)

Participants will be randomized in an approximate 2:1 ratio to participant-collected DBS CMV monitoring with mobile technology support (n=100) or no intervention (n=50). Treatment allocation follows a Block Urn

Design [13] within each stratum. The Block Urn Design treatment allocation method prevents prediction of future treatment allocations and is suitable for unblinded studies. Randomization will be stratified by transplant site and participant's perceived ease of access to blood draw facility (easy or difficult). Randomized participants may withdraw from the study for any reason. If participants withdraw prior to their first scheduled monitoring test, they are eligible for replacement.

Additional participants will be enrolled as retrospective observational controls and will not be randomized (n=450).

Participants in both the randomized and observational cohorts will be entered into the data system after the required demographic and eligibility information were entered.

4.4.4. Replacement of Withdrawals

Participants in the randomized cohort who withdraw prior to their first scheduled monitoring test are eligible for replacement, with the replacement participant receiving a randomized treatment allocation (as opposed to being assigned the same treatment as the participant being replaced).

4.4.5. Selection of DBS Monitoring Interval

Participants in the DBS arm should have conducted DBS monitoring weekly after discharge from transplant center through one-year post-transplant as HCT patients remain at a high risk for late-CMV disease but are no longer in the care of their transplant team.

4.4.6. Blinding

This is an unblinded study.

4.4.7. **Prior and Concomitant Therapy**

At time of randomization, any of the following medications, if applicable, that were administered within 14 days prior to or ongoing at the time of randomization will be recorded:

- Steroids, topical only for GI GVHD and systemic (within 6 weeks prior to randomization)
- PUVA (combination treatment which consists of Psoralens (P) and then exposing the skin to UVA (long wave ultraviolet radiation)
- Immunosuppressant for acute or chronic GVHD (within 14 days prior to randomization, collecting only the start and stop dates)
- Preemptive or prophylaxis antivirals (i.e. dosing of foscarnet, ganciclovir, valganciclovir, cidofovir, brincidofovir, letermovir, acyclovir/valacyclovir [high and low dose], or any other investigational anti-CMV agent) (within 14 days prior to randomization)
- T-cell depleting agents including, but not limited to, ATG, alemtuzumab, etc. (any time after conditioning)

Use of antivirals for CMV treatment, topical steroids for GI GVHD, and systemic steroids during the study period will be recorded during medical chart review at quarterly follow-ups. Participants are expected to continue with their recommended monitoring if they initiate pre-emptive treatment for CMV during the study period.

4.4.8. Intervention Compliance

Participants randomized to the DBS arm will receive training on DBS self-collection prior to discharge from the transplant center. Since the primary objective is to compare monitoring compliance between intervention and standard of care, the study procedures have been designed to limit contact between study staff and participants during the study period.

4.5. Adherence and Safety Variables

4.5.1. Primary Outcome Measures

• The primary outcome is the number of participants in each intervention group who complete >90% of their clinician-recommended CMV monitoring tests in the study period (Section 3.3.2), by 1-year post-transplant.

The proportion of clinician-recommended CMV monitoring tests completed will be defined for each participant as the number of clinician-recommended CMV monitoring tests completed divided by the number of recommended clinician-recommended CMV monitoring tests, where the number of clinician-recommended CMV monitoring tests are defined as in Section 3.3.

The primary outcome measure will be considered a binary variable based on each participant's observed proportion of clinician recommended CMV monitoring tests completed:

- Met > 90% threshold: the participant completed > 90% of their clinician recommended CMV monitoring tests (Success)
- Did not meet > 90% threshold: the participant completed < 90% of their clinician recommended CMV monitoring tests (Fail)

Participants who withdraw prior to discharge will be considered as fail, i.e. not meeting the >90% threshold. Participants who didn't have recommended monitoring test scheduled will also be considered as fail.

The primary and secondary adherence outcomes will be analyzed with ITT, mITT and completer populations during the Study Period defined in Section 3.3.2. A sensitivity analysis will be conducted to exclude all participants from the University of Minnesota for the primary and secondary adherence measures.

In addition, sensitivity analyses with Maximal Study Period defined in Section 3.3.3 will be performed with ITT, mITT and completer populations with and without the participants from the University of Minnesota.

4.5.2. Secondary Outcome Measures

• The total number of recommended clinician recommended CMV monitoring tests that were completed per participant in the study period by 1 year after HCT will be defined as in Section 3.3.

The primary and secondary adherence outcomes will be analyzed with ITT, mITT and completer populations during the Study Period defined in Section 3.3.2. A sensitivity analysis will be conducted to exclude all participants from the University of Minnesota for the primary and secondary adherence measures.

In addition, sensitivity analyses with Maximal Study Period defined in Section 3.3.3 will be performed with ITT, mITT and completer populations with and without the participants from the University of Minnesota.

- The number of participants in the DBS and standard of care arms with possible, probable or proven end-organ CMV disease in the study period by 1 year after HCT will be measured from data entered by clinic staff during medical chart abstraction. Chart abstraction will occur at enrollment, quarterly contacts and at the study close-out visit. Proven/probably breakthrough CMV disease will be considered as a Serious Adverse Event of Special Interest (SAESI).
- Finger-stick procedure-related Grade 3 AEs will be abstracted through medical chart review at quarterly contacts and at the final close-out contact as described in the Manual of Procedures (MOP). Participants will be considered as meeting the outcome measure if they have at least one finger-stick procedure-related Grade 3 AE during the study period.

- CMV prophylaxis for at least 30 days from the day of transplant to 100 days post-transplant
- Participant baseline demographics will be presented for the randomized and observational cohorts. Stratification variables will be presented for the randomized cohort as these were not collected in the observational cohort.
- The number of participants in the randomized and observational cohorts with possible, probable or proven end-organ CMV disease by 1 year after HCT will be reported. These data were collected on the CMV Infection or Disease eCRF at each follow-up.
- The local provider CMV viral load treatment threshold will be reported. These data were entered on the CMV Viral Treatment Threshold eCRF at enrollment or when new thresholds became effective.
- The local provider CMV clinician recommended CMV monitoring intervals will be reported as described (Section 3.3.4, 3.3.5, and 3.3.7).

• The composite scores of different variables of participant and provider satisfactions according to the 5-point Likert scale questionnaires will be reported as described. (Section 3.3.12, 12.2).

5. SAMPLE SIZE CONSIDERATIONS

Power calculations used a binomial distribution to ascertain the number of participants needed to detect a clinically meaningful difference in proportions of participants meeting the primary endpoint [10]. Based on preliminary data, the assumed proportion of individuals completing >90% of their recommended surveillance tests in the standard office-based testing arm would be in the range of 50-55%. In a previously reported clinical trial, high proportions of CMV monitoring completion resulted in the clinically relevant outcome of a low incidence of late CMV disease [1]. To be successful, this proof-of-concept trial needs to demonstrate that similarly high proportions of monitoring can be achieved with participant collected DBS monitoring. With 150 participants, randomized 2:1, there will be 90-96% power to detect an absolute difference in testing proportions of 25-30% between participants in the intervention (80% with >90% adherence rate) and control arms (50% with >90% adherence rate) (Table 2. Although the 2:1 randomization does not result in increased statistical power, randomizations that favor the experimental arm (2:1 or 3:1) appear to increase the appeal to the potential study participant and have been used successfully in several recent multicenter CMV randomized trials [4, 2, 12].

6. GENERAL STATISTICAL CONSIDERATIONS

6.1. General Principles

Continuous variables will be summarized using the following descriptive statistics unless otherwise noted: n (non-missing sample size), mean, standard deviation, median, maximum and minimum. The frequency and percentages (based on the non-missing sample size) of observed levels will be reported for categorical measures unless otherwise noted. In general, all data will be listed, sorted by site, treatment, and participant ID, and when appropriate by visit number within participant. Tables presenting data from more than one intervention arm in the randomized cohort will be structured with a column for each intervention in the order DBS, SOC, All Randomized and will be annotated with the total population size relevant to that table/treatment. Tables presenting data from all enrolled participants will be structured with columns for each intervention for each intervention in the order DBS, SOC, All Randomized not will be annotated with the total population size relevant to that table/treatment. Tables presenting data from all enrolled participants will be structured with columns for each intervention group in the order DBS, SOC, All Randomized, Observational.

6.2. Timing of Analyses

6.2.1. Interim Analyses

The following interim analyses may be conducted prior to the database lock. No additional interim analyses are planned.

- Among the first 50 participants enrolled on the DBS intervention arm, if the lower one-sided 90% confidence interval for the percent of participants experiencing CMV disease by one-year exceeds 8% (operationally 7 out of 50), a DSMB meeting will be convened. The DSMB will be charged with determining whether this exceptionally high rate of CMV disease has plausible clinical explanations related to the participant characteristics, or if it is the result of a failure in the monitoring system, and if so, what the source of the failure is (lack of compliance, failure of the system).
- Additional ad hoc DSMB meetings to review safety events such as UADEs or SAESIs may also be held.

6.2.2. Final Analysis

The final analysis will be performed after database lock.

6.3. Analysis Populations

6.3.1. Intention-to-Treat Analysis (ITT) Population

The Intention-to-Treat population includes all participants in the randomized cohort in the intervention group to which they were randomly assigned, regardless of their monitoring compliance and regardless of subsequent withdrawal or deviation from the protocol. Participants who withdraw before discharge and participants that withdraw after discharge but before their first scheduled in-office CMV monitoring test will be considered as fail, which is not meeting the >90% threshold for the primary adherence analyses.

6.3.2. Modified Intention-to-Treat (mITT) Population

The mITT population will include all participants in the ITT who have at least one result for the number of clinician-recommended CMV monitoring tests and remained enrolled through their first scheduled clinician-recommended CMV monitoring test (e.g., a participant assigned weekly clinician-recommended CMV monitoring at discharge must remain enrolled for at least 1 week after discharge to be included in the mITT

population). Participants will be grouped based on the intervention received, where participants that complete at least one self-collected DBS sample will be grouped in the DBS arm and all other participants will be grouped in the SOC arm. This population will be used as a supplemental analysis for all adherence outcome measures.

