11 STATISTICAL CONSIDERATIONS

11.1 Study Outcome Measures

11.1.1 Primary Endpoint

The primary endpoint will be the proportion of subjects who complete >90% of their recommended CMV monitoring tests by 1-year post-transplant. We will use logistic regression modeling to compare this proportion between subjects randomized to DBS testing versus standard office-based testing. Since randomization will be stratified by transplant site and subject's perceived ease of access to blood draw facility, these factors will be used as adjustment factors in the models.

For each subject, the number of CMV monitoring tests performed will be assessed and the percent of recommended tests will be calculated. Subjects with percent completion >90% will be considered a success with regard to the primary endpoint. The personspecific denominator for the proportion, number of expected CMV monitoring tests, will be variable and dependent on subjects' immunosuppression and hospitalizations during the study. For example, subjects in this study that are highly immunosuppressed a weekly monitoring schedule is generally recommended, often throughout the first year after transplantation. If such a subject were discharged from the primary transplant center at day 100, there would be 38 remaining tests until day 365 after HCT (if the subject is still alive at 1 year). We will assess the actual number of tests performed and calculate the percent of tests (e.g. 36/38 = 94.7%). Another scenario would be for a subject that stopped monitoring and was then re-started on high-dose steroids for treatment of GVHD with resumption of weekly testing, resulting in yet another denominator. Study participants in the DBS arm who are hospitalized during the study should not collect DBS samples while admitted. Rather, admitting hospitals should monitor participants for CMV with plasma CMV DNA PCR testing as recommended for their level of immunosuppression. Those inpatient testing timepoints will not be included in the person-specific denominator.

The primary analysis will be an intent-to-treat (ITT) analysis of all subjects randomized. Another key analysis will be the modified intent to treat analysis of all subjects who had at least one test done after discharge from the primary transplant team.

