APPENDIX C: SCHEDULE OF EVENTS

			In	itial St	tudy Vi	sit ³						
Visit/Contact	Screening ¹	Enrollment ²	Training 1 ⁵	Training 2 ⁶	Training 3 ⁷	Discharge	DBS self- collection	Plasma Collection ⁴	Quarterly Contact 1	Quarterly Contact 2	Quarterly Contact 3	Final Study Visit
Days after HCT	60-180						60-365	60-365	90	180	270	365
Window (days)		N/2	4						±14	±14	±14	(+120)
Confirm informed consent		Х										
Eligibility assessment	X, Z											
Randomization		Х										
Review of medical history		X, Z										
Review of concomitant medication		X, Z				Х			Х	Х	Х	X, Z
Confirm CMV monitoring interval						Χ, Ζ			Х	Х	Х	
Adherence counseling ⁸			Х									
DBS collection and website training ⁹			Y	Y	Y		Y ¹⁰					
Provision of initial study kits						Y						

¹ It is recommended to have screening done approximately one month prior to planned discharge from the primary transplant clinic

² Screening, enrollment, and initial study visit (trainings for DBS arm) may occur on the same day as long as all trainings are completed by subjects with proficiency and confirmed by study personnel prior to discharge from primary transplant clinic.

³ Trainings 1-3 must be completed prior to planned discharge from the subject's primary transplant clinic.

⁴ Confirmatory plasma sample will be collected from DBS arm subjects if they had a CMV positive DBS.

⁵ Training with study staff supervision.

⁶ Training with study staff supervision.

⁷ Training without study staff supervision.

⁸ Adherence counseling should be done on all randomized subjects after enrollment but prior to discharge from primary transplant clinic.

⁹ DBS collection is required at each DBS training visit. Website and mobile technology training may be optional for training 2 and 3 as necessary.

¹⁰ DBS collection starts the week after discharge and ends approximately one-year post-HSCT

DMID Protocol Number 16-0098 CMV DBS Testing in HCT Recipients

Version 5.0 30 June 2022

			In	itial St	tudy Vi	isit ³						
Visit/Contact	Screening ¹	Enrollment ²	Training 1 ⁵	Training 2 ⁶	Training 3 ⁷	Discharge	DBS self- collection	Plasma Collection ⁴	Quarterly Contact 1	Quarterly Contact 2	Quarterly Contact 3	Final Study Visit
Days after HCT		60-180						60-365	90	180	270	365
Window (days)		N/A							±14	±14	±14	(+120)
Kit integrity monitoring ¹¹						Y	Y					
Subject questionnaire ¹²						Y	Y					Y
Provider questionnaire ¹³												Y
Safety monitoring									Х	Х	Х	Х

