6.3.3. Completer Population

The completer population will include all participants in mITT who were not found ineligible after enrollment, remained enrolled at discharge, have clinician recommended CMV monitoring test interval(s) available and completed the study close-out visit which is scheduled to occur 365 days post-transplant. This population is only being used for sensitivity analyses.

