8.2. Secondary Adherence Analyses

A fractional logistic regression model will be fit with quasi-maximum likelihood estimates in the ITT population where the outcome will be the proportion of recommended monitoring tests completed per participant, and the covariates will be randomized intervention group and the stratification variables. This fractional response model was introduced by Papke and Wooldridge (1996) in their frequently cited extension of the generalized linear model to analyze proportion data that are bounded by 0 and 1. Although commonly applied to these outcome data for simplicity, ordinary least squares regression assumes that the predictor variables and continuous outcome variable are linearly related and that the variance is independent of the mean, the violations of which in models of fractional outcomes result in biased estimates and potentially misleading inference. The marginal effects of predictor variables on the mean proportion response can be estimated using the binominal likelihood framework with robust standard errors. Appropriate to the proportion outcome data, the model allows for responses at the 0 and 1 boundaries, in contrast to the beta regression approach that has been described for proportion data that do not include extremes (zero or one).

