To estimate the treatment effect of the DBS intervention on the proportion of recommended tests completed by individuals in the DBS vs SOC group, we will fit the fractional logistic model using SAS PROC GLIMMIX with logit link function and the random residual option to estimate model parameters using a quasi-likelihood function. A two-sided Wald-test for evidence of association between intervention group and proportion of recommended monitoring tests completed will be conducted at the 5% significance level. This analysis will be repeated in the mITT population and the Completer population. The results from the models of the proportion of recommended tests completed will be presented in Table 17. Table 18 presents the results from the sensitivity analysis conducted on the ITT and mITT populations with the maximal possible study period. Table 19 presents the results from the sensitivity analysis conducted on the ITT and mITT populations excluding participants from the University of Minnesota. Example SAS code for this analysis is shown below and specifies the S or SOLUTION option to report the fixed effects parameter estimates, and ILINK option to report estimates on the mean (probability) scale. Variables for transplant site and the participants' perceived ease of access to the blood draw facility will be included as covariates as described in Section 8 for all adherence models.

PROC GLIMMIX DATA=DSN;

MODEL PCT=TRT SITE EASE/ DIST=BINOMIAL LINK=LOGIT S;

RANDOM _RESIDUAL_;

OUTPUT OUT=FRACOUT PRED(ILINK)=PRED LCL(ILINK)=LOWER UCL(ILINK)=UPPER; RUN;

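### SAP 6.3.2 groups the mITT set by intervention received, so DBS-randomised participants with no self-collected sample are analysed as SOC

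*SAP*

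**What the plan says.** SAP 6.3.1 analyses the ITT population in the arm assigned by randomisation. SAP 6.3.2 takes a subset of that population and changes the grouping: "Participants will be grouped based on the intervention received". One or more self-collected DBS samples places a participant in DBS; otherwise "all other participants will be grouped in the SOC arm". The section calls the result a supplemental analysis for all adherence outcomes.

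Protocol 11.1.1 compares subjects according to the arm to which they were randomised. It describes as another key analysis the "modified intent to treat analysis of all subjects who had at least one test done after discharge from the primary transplant team". That defines who is included and does not regroup anyone. SAP section 17, which lists changes to the planned analyses, does not mention regrouping.

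SAP 8.2 specifies the fractional logistic model for the ITT population and states that "the covariates will be randomized intervention group and the stratification variables". It then says: "This analysis will be repeated in the mITT population and the Completer population". SAP 6.3.3 adds that "The completer population will include all participants in mITT" who meet further conditions, with no grouping rule of its own.

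On supply of the intervention, SAP 4.4.2 says: "Participants in the DBS arm will receive DBS self-collection and WB collection kits". On training, a note to Protocol Appendix C says: "DBS collection is required at each DBS training visit".

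**The concern.** Whether someone ever self-collects a sample is known only after randomisation and is itself a monitoring behaviour. It is not the outcome: SAP 3.3.5 and 4.4.1 score success on clinician-recommended tests found at chart review, which both arms complete. It is nevertheless likely to be correlated with that outcome. Since SOC participants receive no kits, the rule in practice takes never-collectors out of DBS and adds them to SOC, which can change both arms' success rates in opposite directions.

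The rows affected are the mITT rows of Tables 14-19 and, if the Completer set inherits the grouping, the Completer rows of Tables 14 and 17. They carry Wald tests at the 5% level and will be read beside the ITT result. Agreement or disagreement with ITT could then come from the regrouping alone. Table 6 lists reasons for exclusion but has no line for participants moved between arms.

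There is also a programming problem. For the SAP 8.2 model, 6.3.2 and 8.2 point to different arm variables, so two programmers could produce different mITT rows in Tables 17-19.

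**Working it through.** **Design figures.** Protocol 11.2 and SAP section 5 plan 100 DBS and 50 control participants, success of 80% against 50%, and two-sided 5% significance. The stated power is 96%, 89% and 80% at control rates of 50%, 55% and 58%. A pooled-variance normal approximation gives 96.2%, 88.5% and 80.4%, so the design inputs are read correctly. No stated number is in dispute.

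**Effect of regrouping.** Let m be the number of the 100 DBS participants who never self-collect, q their success rate, and pD and pS the true success rates by randomised arm. After regrouping:

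- DBS rate = (100·pD − m·q) / (100 − m)
- SOC rate = (50·pS + m·q) / (50 + m)

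The documents give neither m nor q; the values below are assumptions.

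**No true effect (pD = pS = 0.50).** With m = 10 and q = 0: 50/90 − 25/60 = 0.556 − 0.417 = +13.9 points. With m = 10 and q = 0.75: 42.5/90 − 32.5/60 = 0.472 − 0.542 = −6.9 points. Differences in percentage points:

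| m | q = 0 | q = 0.25 | q = 0.50 | q = 0.75 |
|---|---|---|---|---|
| 2 | +2.9 | +1.5 | 0 | −1.5 |
| 5 | +7.2 | +3.6 | 0 | −3.6 |
| 10 | +13.9 | +6.9 | 0 | −6.9 |

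**Rejection rates for the same null case.** These come from simulation with 40,000 trials per scenario and a two-sided Wald log-odds-ratio test, unadjusted for site and ease of access:

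| m | q = 0 | q = 0.25 | q = 0.50 | q = 0.75 |
|---|---|---|---|---|
| 2 | 0.056 | 0.049 | 0.047 | not run |
| 5 | 0.129 | 0.070 | 0.049 | 0.068 |
| 10 | 0.378 | 0.130 | 0.050 | 0.129 |

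A pooled z test gives nearly the same values. By that test, at m = 10 and q = 0.75, 0.128 of the 0.130 rejections favour SOC. When participants were analysed as randomised, the Wald test rejected in 0.036 to 0.050 of trials.

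**Planned effect (pD = 0.80, pS = 0.50; true difference 30 points).** With m = 10 and q = 0: 80/90 − 25/60 = 47.2 points. With m = 10 and q = 0.80: 72/90 − 33/60 = 25.0 points.

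| m | q = 0 | q = 0.25 | q = 0.50 | q = 0.80 |
|---|---|---|---|---|
| 5 | 38.8 | 35.2 | 31.6 | 27.3 |
| 10 | 47.2 | 40.3 | 33.3 | 25.0 |

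**Direction.** Bias toward DBS is more plausible, because people who never self-collect may also skip office tests. It is not certain. SAP 3.3.4 records that the University of Minnesota entered actual tests in place of the recommended schedule. SAP 6.5.2 scores early leavers only on tests due before withdrawal. Some never-collectors may therefore count as successes.

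**The case against.** The strongest reply is that few participants may move. Three training sessions each require a collection, and Protocol 4.1 requires proficiency to be confirmed before discharge. Those who leave before their first scheduled test are outside mITT, and a single sample keeps a participant in DBS. With 2 moved, the tables above show rejection close to nominal. The 38% figure needs 10 never-collectors who all fail. This limits the likely size and stands.

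The textual conflicts can also be read more gently. The covariate sentence in SAP 8.2 describes the ITT model, and repeating it in mITT could mean using the grouping in 6.3.2. SAP 8.1 and the table footnotes say only intervention group. Protocol 11.1.1 has no separate sentence on how mITT participants are grouped, so that conflict rests on its comparison of randomised groups and its lack of any regrouping rule. These readings soften the contradiction but leave the arm variable unsettled.

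As-randomised grouping would not make mITT or Completer fully randomised comparisons, because both select on retention after randomisation. It would remove one further, avoidable source of bias. The mITT membership rules of the two documents would also still differ: the protocol requires a test done, while the SAP requires enrolment through the first scheduled test with a recommended schedule available.

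Finally, Table 5 separates training collections from self-collected samples, and its footnote b ties the latter to samples with laboratory results. That helps, but 6.3.2 does not refer to it, and Table 5 does not report the success rate of those moved.

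**Conclusion.** The concern holds. SAP 6.3.2 applies an as-treated rule under an mITT label. The rule departs from the by-randomised-arm comparison in Protocol 11.1.1 and leaves the arm variable for the mITT rows of Tables 17-19 unsettled against SAP 8.2. The Completer rows are affected by implication only.

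The primary ITT test is not affected, so this is a point to correct and not a threat to the main conclusion. The text is clear; the size of the consequence is not. It depends on two quantities absent from the documents. Over the assumed range of 5 to 10 participants moved, the null difference shifts by between −6.9 and +13.9 points, and two-sided rejection ranges from about 5% to 38%. With 2 moved, or with movers who succeed at the common rate, there is essentially no inflation of type I error.

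**What to change.** In SAP 6.3.2, delete the regrouping sentence and state that mITT and Completer participants are analysed in the arm to which they were randomised. This agrees with the comparison in Protocol 11.1.1 and the covariate in SAP 8.2. Add the same statement to 6.3.3 so that the Completer grouping is not left to inference.

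If an as-received analysis is still wanted, give it its own as-treated label and rows, report the number of participants moved and their success rate, and state whether training collections count as self-collected samples.

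The cost is a one-sentence change in 6.3.2 with a matching line in 6.3.3. No new data are needed and the programming becomes simpler. The separate difference in mITT membership between protocol and SAP is not resolved by this change.
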